## g) Specimen Banking

 Mount Sinai	Protocol Title:	Detection of Liver Fibrosis Using IVIM Diffusion and DCE MRI in HCV
	Principal Investigator Name/Contact Info:	[name]
	Primary Contact Name/Contact Info	[name] [contact] [contact]
	Date Revised:	9/16/2016
	Study Number:	GCO09-1187

N/A

### **h) Data Management and Confidentiality**

All research data will be stored separately from direct identifiers (e.g. name, address, DOB, MRN, SSN) that can link the data to a person's identity. Research data files will be stored using a unique "code" instead. The "linking code file" will be maintained separately in [name] office.

The file that links the code to the person's identity (direct identifiers) will be maintained electronically and in an encrypted file on a departmental network drive in [name]'s office.

All research data files will be stored electronically in encrypted files. Access to the data files will be through restricted view set up by Radiology IT and password protected. The data will be stored for 7 years.

### **i) Provisions to Monitor the Data to Ensure the Safety of subjects**

N/A Minimal risk

### **j) Withdrawal of Subjects**

Subjects may withdraw at any time from the study with no penalty. This will not affect their ability to receive medical care. If a subject withdraws from the study, they must contact the PI in writing. The subject's data may still be used after they have withdrawn authorization.

The study doctor, the sponsor or the institution may stop the subject's involvement in this study at any time without his/her consent. This may be because the study is being stopped, the instructions of the study team have not been followed, the investigator believes it is in the subject's best interest, or for any other reason. If specimens or data have been stored as part of the study, they too can be destroyed without the subject's consent.

## **6) Risks to Subjects**

Approximately two percent (2%) of participants experience some side effects with the use of gadolinium; however, they are mostly mild (nausea, headache, hives, temporary low blood pressure).

### **Risks Associated With Intravenous Catheter Placement:**

*Likely:*

 Mount Sinai	Protocol Title:	Detection of Liver Fibrosis Using IVIM Diffusion and DCE MRI in HCV
	Principal Investigator Name/Contact Info:	[name]
	Primary Contact Name/Contact Info	[name] [contact] [contact]
	Date Revised:	9/16/2016
	Study Number:	GCO09-1187

- Minor discomfort;
- Pain in the injection site.

*Less Likely:*

- Bleeding;
- Infection;
- Bruising.

**Risks Associated With MRI:**

- Anxiety/stress;
- Claustrophobia;
- Discomfort.

Because of the powerful magnetic force of the MRI scanner, a subject may not be able to participate in the study if he/she has:

- Metallic or other surgical implants (for example: pacemaker, heart valves, aneurysm clips, metal plates or pins and some orthopedic prostheses);
- Metal pieces in your eye(s) or other body part(s); or
- Difficulty lying still or inability to lie on your stomach
- Claustrophobia
- Anxiety/stress.

**Risks Associated with Gadolinium**

*Less likely*

- Headaches;
- Nausea.

*Less likely, but serious*

- Allergic reaction.

*Very rare, but serious*

- Nephrogenic systemic fibrosis (NSF)/Nephrogenic Fibrosing Dermopathy (NFD). NSF is a condition associated with the gadolinium contrast agent when there is severe kidney disease. Symptoms include tightening or scarring of the skin and organ failure. In some cases, it can be deadly. NSF has not been seen in patients with normal working kidneys or mild problems in kidney function.

**Reproductive Risk**

If a subject is pregnant or nursing or plans to become pregnant during the course of the study, he/she cannot take part in this research study. We do not know the effects on the fetus, breastfeeding baby, or mother-to-be, and this study may cause harm. A subject should not become pregnant or breastfeed, while on this study. To ensure the safety of subjects, pregnancy

 Mount Sinai	Protocol Title:	Detection of Liver Fibrosis Using IVIM Diffusion and DCE MRI in HCV
	Principal Investigator Name/Contact Info:	[name]
	Primary Contact Name/Contact Info	[name] [contact] [contact]
	Date Revised:	9/16/2016
	Study Number:	GCO09-1187

tests, if pregnancy cannot be excluded by the participant, will be performed prior to any scan for women of child-bearing potential.

All procedures will be explained thoroughly to each subject before they are scanned. The subject will be given an option to listen to music during the scan to help calm their fears and lessen the noise of the MRI scanner. All subjects will be given a call button to push if they need to speak to the technician if they feel anxious.

The loss of confidentiality or privacy is possible, but all scans will be coded with a study ID number and all names, DOB and all other similar data will be removed. The code will be kept in a separate secure location. Every attempt will be made that confidentiality or /privacy will be maintained.

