### **5) Study Design**

#### **a) Recruitment Methods**

Subjects with liver disease will be identified and recruited for the study by their physicians in the Liver Transplant and/or Liver Disease team. This selection will come from the physicians' recommendation, which is familiar with their patient's history. The referring physicians will not be considered co-investigators except [name] and [name]. [name] and [name] are both Co-investigators on this project. They will tell the other physicians in Liver Transplant and Liver Disease about the study and help to enroll patients.

Other sources of potential subjects are the KCC ambulatory procedure list and the Mount Sinai Liver Transplant list provided by the Liver Transplant/Liver Disease Department. Subjects with liver disease who underwent liver biopsy at Mount Sinai will be identified by [name] from the Pathology Department. [name] is a Co-investigator on this study and provides the study team with a quarterly Pathology list.

The treating physician will be the first to notify potential subjects about the study. If subjects consent to be contacted the Research Coordinator will call them to explain the study and to ask if they are willing to be part of this study. No potential subject will be contacted by the study team without subject's prior consent. The study coordinator will review all listings and the patient's medical records to check for their eligibility according to the inclusion/exclusion criteria and contraindications for MRI. A HIPAA waiver of authorization will be requested for the study.

An announcement within the MSSM Broadcast emails will be used for recruitment.

 Mount Sinai	Protocol Title:	Detection of Liver Fibrosis Using IVIM Diffusion and DCE MRI in HCV
	Principal Investigator Name/Contact Info:	[name]
	Primary Contact Name/Contact Info	[name] [contact] [contact]
	Date Revised:	9/16/2016
	Study Number:	GCO09-1187

*ResearchMatch will also be used as a method for identifying and contacting potential subjects. The study specific announcement is included with this submission.*

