### **Exclusion criteria**

1. Age less than 18 years
2. Unable or unwilling to give informed consent
3. Contra-indications to MRI
  - a. Electrical implants such as cardiac pacemakers or perfusion pumps
  - b. Ferromagnetic implants such as aneurysm clips, surgical clips, prostheses, artificial hearts, valves with steel parts, metal fragments, shrapnel, tattoos near the eye, or steel implants
  - c. Ferromagnetic objects such as jewelry or metal clips in clothing
  - d. Pregnant subjects
  - e. Pre-existing medical conditions including a likelihood of developing seizures or claustrophobic reactions.

As with all subjects referred for MRI, each subject is screened for possible contraindications with a routine questionnaire.

Subjects with GFR <30 will not undergo DCE-MRI with Gadolinium contrast. For subjects with GFR <30, we will still consider enrolling them for a non-contrast MR protocol, including non-contrast sequences, FibroScan and/or ARFI and blood tests. Subjects with GFR between 30 and

	Protocol Title:	Detection of Liver Fibrosis Using IVIM Diffusion and DCE MRI in HCV
	Principal Investigator Name/Contact Info:	[name]
	Primary Contact Name/Contact Info	[name] [contact] [contact]
	Date Revised:	9/16/2016
	Study Number:	GCO09-1187

60 will receive only either a half dose Multihance or Gadoxedate disodium (Eovist), and will not have repeat DCE-MRI studies with Gadolinium contrast. Only subjects with GFR  $\geq 60$  will be proposed to return for repeat DCE-MRI studies with Gadolinium contrast. Subjects with GFR  $< 60$  will be considered to return for repeat non-contrast MRI-studies.

We will consider injecting gadolinium contrast in healthy volunteers, for the purpose of DCE-MRI image optimization.

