## 14) Vulnerable Populations

Economically or socially disadvantaged persons are eligible for the study if the Principal investigator believes that they will be good candidate. The study will be carefully explained and discussed with the patient. Any questions that the patient has will be explained thoroughly to both the satisfaction of the principle investigator as well as the patient. We do not wish to enroll

 Mount Sinai	Protocol Title:	Detection of Liver Fibrosis Using IVIM Diffusion and DCE MRI in HCV
	Principal Investigator Name/Contact Info:	[name]
	Primary Contact Name/Contact Info	[name] [contact] [name]
	Date Revised:	9/16/2016
	Study Number:	GCO09-1187

any person who is does not fully understand what is involved in this study, nor do we wish to improperly influence any participant.

In order to protect the rights and welfare of subjects, we will **not** preferentially enroll vulnerable subjects. In order to protect the rights and welfare of subjects, we will provide information to the subjects that they can fully understand, and similarly write the consent document in a simple manner and language that someone with sixth grade language could comprehend.

Pregnant subjects are excluded from participation in this study because of the possible effect of gadolinium to the fetus.

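### Section 6 bars pregnant, nursing and pregnancy-planning subjects, but the exclusion list used for screening names pregnancy only

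*Combined protocol and SAP*

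**What the plan says.** Section 6, under Reproductive Risk, states a rule on participation. Its condition reads "If a subject is pregnant or nursing or plans to become pregnant during the course of the study"; anyone who meets it is barred from the research. The reason given is that effects on the fetus, the breastfed baby and the mother-to-be are unknown and that harm is possible. A rule on conduct follows: "A subject should not become pregnant or breastfeed, while on this study".

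Section 5b lists the exclusion criteria. The only reproductive entry is "d. Pregnant subjects", placed under contraindications to MRI. The inclusion criteria in the same section contain no reproductive condition. Section 14 returns to the subject and says "Pregnant subjects are excluded from participation in this study because of the possible effect of gadolinium to the fetus".

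On how eligibility is established, Section 5a has the study coordinator go through the listings and medical records to "check for their eligibility according to the inclusion/exclusion criteria and contraindications for MRI". Section 5b adds that "each subject is screened for possible contraindications with a routine questionnaire". Sections 5f and 6 provide for a pregnancy test before any scan in women of child-bearing potential when pregnancy cannot otherwise be excluded.

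**The concern.** An eligibility rule works only if it appears where eligibility is checked. Here the fullest statement of the reproductive exclusions is in the risk section, and the list that the coordinator is told to apply is shorter. Someone who follows Section 5a to the letter has no prompt to ask about nursing or planned pregnancy.

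What is at stake is a protection that the protocol itself sets out on safety grounds. Section 5f makes gadolinium-enhanced MRI the default, and Section 5b leaves open giving contrast to healthy volunteers. A subject who is missed at screening could therefore be exposed, and her enrolment would breach Section 6.

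**Working it through.** No arithmetic is needed beyond a count, and the plan gives no figure to reproduce. The check sets side by side every place where the protocol deals with reproductive status or eligibility screening.

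| Place in protocol | Pregnant | Nursing | Planning pregnancy |
|---|---|---|---|
| Section 6, Reproductive Risk | barred | barred | barred |
| Section 5b, exclusion item 3d | excluded | not mentioned | not mentioned |
| Section 5b, inclusion criteria | not mentioned | not mentioned | not mentioned |
| Section 14, Vulnerable Populations | excluded | not mentioned | not mentioned |
| Sections 5f and 6, test before scans | tested, conditionally | not detectable | not detectable |

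1. Section 6 bars three conditions. The exclusion list carries one. That leaves 3 − 1 = 2, nursing and planned pregnancy, which appear in no eligibility or screening text.

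2. Section 5a does not add to the list. It refers the coordinator to the inclusion/exclusion criteria and to MRI contraindications, and the contraindications set out in Section 5b again include pregnancy only.

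3. The pregnancy test does not close the gap at entry. It detects a current pregnancy, and it is done only when pregnancy cannot be excluded by other means. It carries no information about nursing or intention.

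4. Exposure follows for most subjects, but not all. Contrast is the default under Section 5f. Under Section 5b, subjects with GFR below 30 have a non-contrast protocol, and those between 30 and 60 have restricted contrast and no repeat contrast study. The bar in Section 6 covers taking part at all, so the mismatch in the text also applies to subjects who receive no contrast.

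5. Two further points of contact with subjects might catch the omission: the routine MRI questionnaire, whose content the protocol does not give, and the consent form, which is not in the review copy. Neither can be counted as a safeguard or as a failure.

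**The case against.** The strongest reply is that this is an omission and not a contradiction. Section 6 belongs to the same protocol and is unqualified. Sections 5b and 14 are silent on nursing and planned pregnancy; they do not permit them. Read as a whole, the protocol has one rule, and the fault lies in where it is placed. That is fair as a description. It does not remove the problem, because Section 5a directs the eligibility check to the criteria list and not to the risk section.

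A second reply is that other steps may catch these subjects. Every subject completes a questionnaire, and Section 12 has trained study staff take consent before the MRI. This stands as a limit on the conclusion. A reader might infer that every nursing woman or woman planning pregnancy who is screened would be passed; the documents do not support that, because the content of the questionnaire and of the consent form is unknown.

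A third reply concerns repeat visits. A reader might infer that a woman who conceives between visits, for example before the scan 3 to 6 months after antiviral therapy, would go unnoticed. The test applies before any scan, so that case is partly covered, though only conditionally. Nursing is the condition that the described checks leave most clearly open.

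Nor do the documents show that volunteers reached by broadcast email or ResearchMatch are at greatest risk. The check quoted from Section 5a is a review of listings and medical records, and the section does not say how respondents to those announcements are screened.

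**Conclusion.** The point holds as an inconsistency in the eligibility text. Applied as written, the exclusion list does not enforce two of the three reproductive exclusions in Section 6. A barred subject could be enrolled and, by default and subject to the GFR limits, given gadolinium, unless the questionnaire or the consent form intervenes.

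The conclusion assumes that the coordinator works from the list, as Section 5a says. It makes no assumption about the documents that are not available. The size cannot be stated: the protocol does not give the age and sex mix, so neither a large nor a very small number of affected subjects can be claimed. The endpoint, the reference standard, the comparisons and the sample size are unaffected. The point merits correction because it bears on subject safety and the remedy is slight.

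**What to change.** Reconcile Section 5b (exclusion criteria), Section 6 (Reproductive Risk) and Section 14 (Vulnerable Populations), so that the list used for screening and the risk section state the same reproductive exclusions. Which version stands is for the responsible clinicians to decide; this review takes no position on it.

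The change is about one line of text, with no consequence for the analysis. It need go no further: the inconsistency can be resolved without adding new screening steps or rewriting a questionnaire that the documents do not show.

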## 7) Provisions for Research Related Injury

In the event of injury resulting from a subject's participation in this study, the facilities at Mount Sinai Hospital and professional attention will be made available to the subject at his/her expense. Financial compensation from Mount Sinai will not be provided.

## 8) Potential Benefits to Subjects

The subjects may not receive any direct benefit from participation in this research study. Others may not benefit either. However, possible benefits to others include decreasing the numbers of invasive biopsies, which will potentially enable earlier diagnosis of liver damage.

## 9) Provisions to Protect the Privacy Interests of Subjects

Every effort will be made by the investigators and study coordinators to keep all the information in this study strictly private, including subjects' personal information, from the time participants are identified for recruitment until they complete study participation. This includes communication when scheduling appointments, leaving phone messages and follow-up contact. Records of participation, progress and images taken while on the study will be kept secure at Mount Sinai and in a computer file at the sponsor's headquarters. All data sent to the sponsor over the internet will be coded.

All efforts will be made to make the subjects feel at ease with the research situations. They will have the opportunity to ask questions and will have ample time to review and think about any questions, examinations and procedures in the study. Research procedures will be explained in simple, clear, concise language. Members of the research team will be appropriately able to approach prospective participants about the study because the potential subjects may be eligible for enrollment, their physicians have referred them for potential enrollment, and the research team is knowledgeable about study guidelines and protocol.

 Mount Sinai	Protocol Title:	Detection of Liver Fibrosis Using IVIM Diffusion and DCE MRI in HCV
	Principal Investigator Name/Contact Info:	[name]
	Primary Contact Name/Contact Info	[name] [contact] [contact]
	Date Revised:	9/16/2016
	Study Number:	GCO09-1187

## 10) Economic Impact on Subjects

The subject will incur no extra costs, the scans that are part of the standard of care will be submitted to their insurance and other scan time or scans that are part of the study will be paid for by the study sponsor.

## 11) Payment to Subjects

Subjects will be compensated \$40 for each completed scan (up to four, potentially), for travel related expenses. Subjects who do not incur travel related expenses in order to participate do not qualify for compensation.

## 12) Consent Process

Subjects will be given the consent form by their physician to read and take home to think about and then call the research team to make an appointment if they would like to be part of the study. They will be given the opportunity to review the consent document at home, discuss it with whomever they like, think about the information that has been presented to them and be able to make an informed decision, without being concerned or be in any kind of anxiety provoking situation as to whether they wish to participate.

Patients being called by the Research Coordinator will be given the opportunity to ask any questions or mention any concerns about the study and to call back with their decision or any further questions. They will be given time to think about the information that has been presented to them over the phone and they will be offered to receive the consent form prior to a decision whether to take part or not.

All subjects will be consented in Radiology Department before they undergo the MRI examination after they have been given time to review and consider being part of the study. Consent will be obtained by only the members of the study team who have been trained properly and not by referring physicians who are not part of the study team. The subject will be provided with a copy of the signed consent form.

## 13) Process to Document Consent in Writing

We will make the subjects chart with the date that each subject is consented.

## 14) Vulnerable Populations

Economically or socially disadvantaged persons are eligible for the study if the Principal investigator believes that they will be good candidate. The study will be carefully explained and discussed with the patient. Any questions that the patient has will be explained thoroughly to both the satisfaction of the principle investigator as well as the patient. We do not wish to enroll

 Mount Sinai	Protocol Title:	Detection of Liver Fibrosis Using IVIM Diffusion and DCE MRI in HCV
	Principal Investigator Name/Contact Info:	[name]
	Primary Contact Name/Contact Info	[name] [contact] [name]
	Date Revised:	9/16/2016
	Study Number:	GCO09-1187

any person who is does not fully understand what is involved in this study, nor do we wish to improperly influence any participant.

In order to protect the rights and welfare of subjects, we will **not** preferentially enroll vulnerable subjects. In order to protect the rights and welfare of subjects, we will provide information to the subjects that they can fully understand, and similarly write the consent document in a simple manner and language that someone with sixth grade language could comprehend.

Pregnant subjects are excluded from participation in this study because of the possible effect of gadolinium to the fetus.

## **15) Multi-Site Human Research (Coordinating Center)**

N/A

## **16) Community-Based Participatory Research**

N/A

## **17) Sharing of Results with Subjects**

The results of the research portion of MRI (including the MR Elastography), the FibroScan, the ARFI and blood tests (part of the research portion) results will not be given to the subject. However, during the participation in this study, the subjects will have access to any study information that is part of their medical record. The investigator is not required to release research information that is not part of the medical record. Results of the MRI scans will be accessible in the Mount Sinai electronic medical record.

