## Brief Summary of Research (250-400 words):

### 1) Objectives:

#### *Research Question:*

#### MAIN HYPOTHESES

1. IVIM, DCE-MRI and MRE metrics can non invasively discriminate severe fibrosis/cirrhosis (F3-F4), from no fibrosis (F0) and intermediate fibrosis (F1-F2). To test our hypothesis, we will prospectively determine in a cohort of 100 subjects (including 80 with chronic liver disease and 20 controls) whether IVIM DW-MRI, DCE-MRI and MRE parameters are valid markers of liver fibrosis, using histopathology from liver biopsy or explant as the reference.
2. MRI has equivalent performance to ultrasound elastography [including TE (transient elastography, Fibroscan) and ARFI (Acoustic Radiation Force Impulse imaging, Siemens) and serum markers for staging liver fibrosis, with the advantage of being more comprehensive and by providing whole liver coverage.

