## **b) Inclusion and Exclusion Criteria**

### **Inclusion criteria**

Study group

- 1) Chronic liver disease (including viral hepatitis, alcoholic hepatitis, non alcoholic steatohepatitis, primary biliary cirrhosis, primary sclerosing cholangitis, etc.)
- 2) 18 years of age and older
- 3) Patient is able to give informed consent for this study and agrees to provide a blood sample  
Patients preferably (but not necessarily) underwent/will undergo:
- 4) Liver biopsy (percutaneous or transjugular or surgical) performed within 6 months, as part of routine clinical care and/or
- 5) Liver transplant or liver resection performed as part of routine clinical care and/or
- 6) Medical therapy for portal hypertension or TIPS placement as part of routine clinical care and/or

Antiviral therapy for HCV infection.

Control group

- 1) Patients without history of liver disease and healthy volunteers
- 2) 18 years of age and older
- 3) Subject is able to give informed consent for this study and agrees to provide a blood sample

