### f) Procedures Involved in the Human Research

#### Visit 1

Blood test – GFR measurement to be done to evaluate renal insufficiency, liver serum markers, and pregnancy if applicable will be done for research - takes about 10 minutes. DW-MRI and DCE-MRI (MRI with intravenous contrast only if GFR>30) is standard of care and added MRE which is research will be 5 extra minutes (the entire MRI will take about 45 minutes)

Fibroscan and/or ARFI to determine liver stiffness will be done for research - takes about 10-20 minutes.

Visit 1 should take about 60-90 minutes.

Patients under medical treatment for portal hypertension or TIPS procedure are considered to be scheduled for visit 1 before they start their portal hypertension treatment or get TIPS placement.

#### Visit 2

DW-MRI and DCE-MRI (MRI with intravenous contrast only if GFR  $> 60$ ) with MRE sequences is done for research and done for reproducibility and will take another 45 minutes to complete to the first 30 subjects. This visit will take place within a week after visit 1.

This visit may have another blood test and another Fibroscan and/or ARFI so the entire visit should take about 60-90 minutes.

	Protocol Title:	Detection of Liver Fibrosis Using IVIM Diffusion and DCE MRI in HCV
	Principal Investigator Name/Contact Info:	[name]
	Primary Contact Name/Contact Info	[name] [contact] [contact]
	Date Revised:	9/16/2016
	Study Number:	GCO09-1187

Patients under medical treatment for portal hypertension or TIPS procedure are considered to be scheduled for visit 2 after they started their portal hypertension treatment or got TIPS placement to look at changes in hepatic flow and liver stiffness.

Patients starting antiviral therapy for HCV will be evaluated before they start the therapy, and will be repeated 3 to 6 months after the end of therapy.

We would like to perform the following sub-studies: All subjects will receive by default Gd-BOPTA (Multihance, Bracco) enhanced MRI (half dose at 0.05 mmol/Kg for the perfusion study) at 1.5T or 3T. In addition, the subjects may receive one of the following options:

**Option 1:** 1.5T MRI using (Gadoxedate disodium (Eovist)) will be performed in up to 10 subjects.

- Sub-arm 1: In up to 5 subjects receiving Gadoxedate disodium (Eovist), the studies will be repeated twice at least 24h apart to measure reproducibility of DCE-MRI using Gadoxedate disodium (Eovist)

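### Histology is optional, left to routine care and may follow an MRI whose results are in the record, so for patients not already biopsied both getting a reference stage and the staging itself can depend on the MRI

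*Combined protocol and SAP*

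**What the plan says.** All references are to the combined protocol and SAP.

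- **Reference standard.** Section 1, Main Hypothesis 1, tests the MRI parameters "using histopathology from liver biopsy or explant as the reference".
- **Not required, and either order allowed.** The study-group inclusion criteria in section 5b introduce the histology routes with "Patients preferably (but not necessarily) underwent/will undergo".
- **Decided outside the study.** Biopsy is "performed within 6 months, as part of routine clinical care", with no statement that the six months run before or after the MRI. The explant and resection route reads "Liver transplant or liver resection performed as part of routine clinical care and/or".
- **Status of the MRI.** Section 5f, Visit 1, says the DW-MRI and DCE-MRI examination "is standard of care and added MRE which is research will be 5 extra minutes".
- **Visibility.** Section 17 says "Results of the MRI scans will be accessible in the Mount Sinai electronic medical record". The same section says that "The results of the research portion of MRI (including the MR Elastography), the FibroScan, the ARFI and blood tests" results are not given to the subject. It does not say whether treating physicians can see them.

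The document supplied has no statistical analysis section, no definition of the set of patients used for accuracy, no plan for patients without a stage, and no statement that the stage is read without knowledge of the MRI.

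**The concern.** Two separate biases are possible. The first is verification bias. If the physician who decides on biopsy has seen the MRI report, the patients who end up with a stage are partly selected by the MRI. Sensitivity and specificity calculated in staged patients alone then differ from those in the patients enrolled. The second is review bias: a pathologist who can open the MRI report before staging may be influenced by it, which would inflate agreement.

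Both bear on Main Hypothesis 1 (accuracy for F3-F4). They also bear on Main Hypothesis 2, which claims performance equivalent to transient elastography (TE), ARFI and serum markers. If selection follows one test more closely than another, two equally good tests can look different. Selection by MRI is foreseeable here, because the protocol's stated aim is a test that reduces the number of biopsies. Without a record of which came first, the bias could be neither shown nor excluded afterwards.

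**Working it through.** The plan gives no figure to reproduce: no alpha, power, target accuracy, cut-off or verification rate. The numbers below are illustrations on assumed inputs.

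**Step 1. Assumptions.** True sensitivity (Se) and specificity (Sp) of MRI are both 0.80. A share v+ of MRI-positive and v− of MRI-negative patients receive histology, and the decision depends on nothing else.

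**Step 2. Formulas among verified patients.**

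- Apparent Se = Se·v+ / [Se·v+ + (1−Se)·v−]
- Apparent Sp = Sp·v− / [Sp·v− + (1−Sp)·v+]

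**Step 3. Results.**

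| v+ | v− | Apparent Se | Apparent Sp |
|---|---|---|---|
| 0.7 | 0.7 | 0.800 | 0.800 |
| 0.8 | 0.5 | 0.64/0.74 = 0.865 | 0.40/0.56 = 0.714 |
| 0.9 | 0.4 | 0.72/0.80 = 0.900 | 0.32/0.50 = 0.640 |
| 0.5 | 0.9 | 0.40/0.58 = 0.690 | 0.72/0.82 = 0.878 |

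Equal rates give no bias. The sign reverses when a positive MRI takes the place of a biopsy.

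**Step 4. An equally good comparator.** Assume TE also has Se = Sp = 0.80, that both tests are binormal, that they correlate 0.5 within disease class, and that only the MRI drives verification. Simulation gives apparent TE values of 0.819/0.775 at rates 0.8/0.5 and 0.829/0.753 at 0.9/0.4.

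- Sensitivity gap in favour of MRI: 0.865 − 0.819 = 0.046, and 0.900 − 0.829 = 0.071.
- Specificity gap against MRI: 0.775 − 0.714 = 0.061, and 0.753 − 0.640 = 0.113.

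**Step 5. The same model on the AUC scale.** The true AUC is 0.883 for both tests. At 0.8/0.5 the apparent MRI and TE values are 0.879 and about 0.880; at 0.9/0.4 they are 0.871 and 0.876. The largest shift is 0.883 − 0.871 = 0.012, and the two tests differ by about 0.005 or less, against MRI. Verification bias mostly moves patients along the ROC curve rather than shifting the curve.

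**Step 6. Can it be corrected?** Take 100 F3-F4 patients and 100 others, with rates 0.8/0.5. Verified MRI-positives are 64 diseased and 16 not; verified MRI-negatives are 10 diseased and 40 not. The Begg-Greenes correction applies the diseased shares (64/80 = 0.8 and 10/50 = 0.2) to all 100 MRI-positive and all 100 MRI-negative patients. This gives 80 and 20 diseased, so Se = 80/100 = 0.80; Sp likewise returns to 0.80. It works only if verification depends on the recorded MRI result alone, and if that result is kept for unverified patients.

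**The case against.** The strongest reply is that the route from index test to biopsy is inferred. The tests under study are quantitative IVIM, DCE and MRE parameters. Section 17 separates the research portion of the MRI, including MRE, from the scan results in the record, and it recognises research information outside that record. What reaches the physician is most naturally a clinical report, which only partly tracks those parameters. This stands. It makes the figures above upper-end illustrations, and it weakens the case for MRE most. It does not remove the dependence for the DW and DCE examination, which the protocol itself calls standard of care.

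Second, part of the cohort is immune. Section 5a recruits from a pathology list of patients already biopsied, and a study MRI cannot change whether they were verified. This also stands. But it is one route among several, and section 5b admits later histology.

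Third, a reader might infer that the bias must flatter MRI, or that it acts on MRI and spares TE, ARFI and serum markers because those results are withheld. The documents support neither. Overstated sensitivity with understated specificity requires MRI-positives to be verified more often; the last row of the table shows the reverse. Even in the unfavourable cases, MRI loses more specificity than it gains in sensitivity relative to TE. Section 17 withholds the comparator results from the subject and is silent about clinicians.

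Fourth, the protocol fixes neither a cut-off nor an accuracy measure. If AUC is the measure, the distortion is small. That is correct for verification bias; it says nothing about a stager who has seen the MRI.

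**Conclusion.** The point holds in a limited form. As written, the plan allows the MRI to influence who receives a reference stage and how that stage is read, for patients whose histology had not been done or decided before Visit 1. How many patients that is, which way the bias runs and how large it is cannot be derived from the documents.

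Under the assumed rates, sensitivity and specificity at a cut-off could move by roughly 0.07 to 0.16 (0.865 − 0.80 up to 0.80 − 0.64), in either direction. False gaps against an equally good TE would be about 0.05-0.07 in sensitivity and 0.06-0.11 in specificity, with an AUC gap of about 0.005 or less. These figures rest on the binormal model, a correlation of 0.5, and verification that follows the evaluated MRI result directly and TE not at all. The matter deserves a change because it touches both main hypotheses and is cheap to control in advance. It is not evidence that the study's results will favour MRI.

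**What to change.** 1. **Section 5b.** Record the date on which the biopsy, resection or transplant was done or ordered, relative to the Visit 1 MRI. Keep all histology-verified patients in the main analysis. Prespecify a sensitivity analysis for Hypotheses 1 and 2 limited to those whose histology was done or ordered before the MRI. Making that subset primary would give cleaner verification, but at the loss of an unknown share of the 80 patients planned in Main Hypothesis 1, so a sensitivity analysis is the better balance.
2. **Analysis plan.** Report the number of patients without a stage by MRI result. Add a verification-bias-corrected analysis: Begg-Greenes for any binary cut-off, and inverse-probability weighting for AUC or continuous parameters. State the assumption that verification depends only on recorded variables.
3. **Section 17.** Keep research-only quantitative IVIM, DCE and MRE values out of the record until the fibrosis stage is entered, and have the stage assigned without sight of study MRI values. State also whether treating physicians can see FibroScan, ARFI and research blood results. The clinical MRI report, the reporting of incidental findings and the decision to biopsy stay as they are.

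The cost is one date field, a few sentences, a little more analysis and lower precision in the sensitivity subset. A pathologist could still open the clinical report, so the blinding in item 3 is partial and should be described as such.
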